## **List of Abbreviations**

AE: Adverse Event CI: Confidence Interval CL: Cervical Length HIPAA: Health Insurance Privacy and Portability Act of 1996 IRB Institutional Review Board PTB: Preterm Birth RCT: Randomized Controlled Trial SAE: Serious Adverse Event TVU CL: Transvaginal ultrasound cervical length UIC: Ultrasound indicated cerclage

# Study Summary

Title	Cervical cerclage for preventing spontaneous
	preterm birth in twin pregnancies with
	transvaginal ultrasound cervical length ≤ 15mm:
	a study protocol for a randomized clinical trial
Short Title	Cerclage for Twins with short cervix
Methodology	Multi-center, open label, randomized trial
Study Duration	3 years for subject enrollment, and an additional
	6 months for analysis and manuscript
	preparation: 2017-2021
Study Center	Thomas Jefferson University
Objectives	The primary objective of this study is to
	determine if ultrasound indicated cerclage
	reduces the incidence of spontaneous preterm
	birth in asymptomatic women with twin
	gestations with transvaginal ultrasound cervical
	length ≤ 15mm before 24 weeks of gestation.
Number of Subjects	200
Diagnosis and Main Inclusion Criteria	Women, age older than 18, with a twin gestation
	and transvaginal ultrasound cervical length
	≤15mm between 16 to 23 6/7 weeks gestation
Study Product and Planned Use	Cervical cerclage
Reference therapy	Standard obstetrical care include daily vaginal
	progesterone 400mg from diagnosis of cervical
	length ≤25mm (usually 20 weeks) to 36 weeks
Statistical Methodology	Statistical analysis will be based on the intention-
	to-treat principle. The risk of spontaneous
	preterm birth before 34 weeks will be quantified
	by use of the odds ratio and 95% CI. Multivariate
	analysis will be performed using logistic
	regression.
	1

#### **1** Introduction

This document is a protocol for a human research study.

#### 1.1 Background

The incidence of preterm birth (PTB) in the United States is 9.63% with 390,000 deliveries occurring at less than 37 weeks gestation annually, however the incidence of early preterm (less than 34 weeks) have remained steady at 2.76%, with this being the most vulnerable neonatal group. Risk factors for spontaneous preterm births include a previous preterm birth, multiple pregnancies, black race, smoking, periodontal disease, low maternal body-mass index and short cervical length.

In 2015, the twin birth rate was 33.5 twins per 1000 total births. The twin birth rate increased steadily by 76% overall from 1980 to 2009. The number of twin births has risen substantially due to the increased use of assisted reproductive technology. Twin pregnancies have 59% incidence of PTB before 37 weeks and 10.7% incidence of PTB < 32 week, 10 times more at risk of low birth-weight infants (LBW) and had 5 times more risk of early neonatal death. The increased rate of preterm birth in twins is associated with increased neonatal morbidity and mortality rates. Disorders related to short gestation and LBW (low birth weight) is the second cause of infant death (17.2%).

In singleton pregnancies with risk factors for PTB, effective medical interventions have been identified to reduce the risk of recurrent PTB. In women with singleton pregnancy and history of PTB, weekly treatment with intramuscular 17-alpha hydroxyprogesterone caproate beginning at 16-20 weeks gestation until 36 weeks and ultrasound indicated cervical cerclage for women with transvaginal ultrasound cervical length (TVU CL)  $\leq$  25mm identified before 24 weeks of gestation have shown effective to decrease PTB by 44% and 30% respectively. Women with singleton pregnancy with no history of PTB and incidental finding of cervical length  $\leq$ 25mm before 24 weeks of gestation will benefit from vaginal progesterone.

Similar to singleton pregnancy, in twin pregnancy TVU CL  $\leq$ 25mm before 24 weeks of gestation identify women at risk of preterm birth. For example the calculated risk of PTB <36 week for a twin pregnancy with TVU CL  $\leq$ 25mm at 20 weeks is 83% while TVU CL  $\leq$ 15mm at the same gestational age is 94%, and the calculated risk of PTB < 32 weeks is 69% and 78% respectively. Several randomized clinical trials have evaluated the effectiveness of 17-alpha hydroxyprogesterone caproate,  vaginal progesterone, pessary or ultrasound indicated cervical cerclage in women with twin pregnancy TVU CL less than 25mm before 24 weeks with no significant difference between study vs control group. However, to date, no trial has evaluated the potential benefit of a cerclage in twins, specifically for women with a TVU CL  $\leq$ 15mm

## 1.2 Clinical Data to Date

**Pessary:** 

A recent pessary trial conducted on women with twin pregnancy and TVU CL < 30mm at three institutions (TJUH, University of Pennsylvania and Naples, Italy) showed no significant decrease in the incidence of preterm birth <34 weeks or improvement in the perinatal outcome. Other similar trials in USA and Europe have shown conflicting results. A meta-analysis evaluating all available studies concluded that the use of the pessary in twin pregnancies with short TVU CL at 16-24 weeks does not prevent SPTB or improve perinatal outcome.

#### Vaginal progesterone:

An Egyptian randomized clinical trial of twin gestation with TVU CL 20-25 mm between 20 to 24 weeks of gestation using daily 400mg vaginal progesterone versus no progesterone showed a significant 33% and 60% decrease in preterm labor <34 week: 41/116 (35.3 %) vs 57/108 (52.8 %) RR: 0.67 (0.49–0.90) and preterm labor <32 week: 14/116 (12.1 %) vs 32/108 (29.6 %) RR: 0.40 (0.23–0.72) respectively and 33% decreased in neonatal respiratory distress: 82/229 (35.8 %) vs 111/210 (52.9 %) RR: 0.67 (0.54–0.84).

A recently published meta-analysis and individual patient database including 303 women (159 assigned to vaginal progesterone, 144 assigned to placebo/no treatment) and their 606 infants from six randomized controlled trials) concluded that the use of daily 400mg of vaginal progesterone in women with twin pregnancy and TVU CL  $\leq$  25 mm decreased the risk of preterm birth <34 week and <32 weeks by 29% and 49% respectively and decreased on composite neonatal morbidity and mortality by 47%: 23/84 (27.3%) vs 28/70 (40%) RR: 0.57 (0.36-0.93). This therapy seems to be more effective in twins with TVU CL 20 to 25mm (n=207) and maybe useful between 10-19mm (n=84), but a significant decrease in preterm birth was not seen when TVU CL is <10 mm (n=14), however the sample size in these last two subgroups were too small to conclude.

Based on this new information, we at the Maternal Fetal Medicine Division at TJUH considered that there is enough evidence to initiate routine screening for preterm birth with TVU CL in women with twin pregnancies from 18 to 24 weeks and to offer daily 400mg of vaginal progesterone to those women with TVU CL  $\leq$  25mm as a standard practice since February 2017.

## 1.3 Risk/Benefits

The major risks of ultrasound indicated cerclage that have been reported in previous studies involving singleton pregnancies include intraoperative rupture of membranes (less than 1%), cervical laceration, cervical bleeding, chorioamnionitis (undiagnosed at the time of cerclage or acquired post cerclage placement), failure to place the cerclage and failure of the cerclage on prolonging pregnancy with possible pregnancy loss or delivery at a periviable gestational age around 23-25 weeks of gestation. Other risks are those associated with anesthesia during the surgical procedure: hypotension, allergy to medications, headache. To limit these risks, the anesthetic route is typically regional anesthesia. Later on during the course of pregnancy, other risks maybe present as preterm contractions with the cerclage in place may cause laceration of the cervix and bleeding in which case the cerclage needs to be removed.

Minor side effects include increased vaginal discharge, there is a theoretical disruption the vaginal flora associated with foreign object, and minimal discomfort at the time of cerclage removal.

The potential benefits include prolongation of pregnancy, decreased very preterm delivery (< 28 weeks), very low birth weight (<1500 grams) and decreased in composite morbidity for the newborn (respiratory distress syndrome, need of intubation and mechanical ventilation, intraventricular hemorrhage, necrotizing enterocolitis, sepsis and retinopathy of the preterm newborn) and length of admission in the neonatal intensive care unit. Decreased perinatal mortality. These potential benefits are based on results of previous retrospective cohorts available in twin pregnancies.

All of the investigators have received formal training on ultrasound indicated cerclage placement. The training and experience of the investigators will minimize the risks associated with cerclage placement.

Our protocol specifically states that the cervical cerclage will be removed if the patient goes into labor, has preterm premature rupture of membranes (PPROM), presents with active cervical bleeding, or if she remains asymptomatic and reaches 36 weeks of gestation.

#### 2 Study Objectives

The overall objective of this study is to assess the efficacy of the use of ultrasound indicated cerclage for prevention of preterm birth in a population of women with twin gestations and TVU CL  $\leq$  15 mm prior to 23 6/7 weeks.

## 2.1 Primary Objective

The primary objective of this study is to determine if ultrasound indicated cerclage reduces the incidence of spontaneous PTB before 34 weeks in asymptomatic women with twin gestations and TVU  $CL \le 15$  mm between 16 0/7 to 23 6/7 weeks of gestation.

#### 2.2 Secondary Objective

To determine if ultrasound indicated cerclage reduces the incidence of spontaneous PTB before 24, 28 and 32 weeks in asymptomatic women with twin gestations and TVU CL  $\leq$  15 mm between 16 0/7 to 23 6/7 weeks of gestation.

To determine if ultrasound indicated cerclage reduces the neonatal mortality and morbidity in asymptomatic women with twin gestations and TVU CL  $\leq$  15 mm between 16 0/7 to 23 6/7 weeks of gestation. Neonatal morbidity will include any of the following (composite neonatal outcome): respiratory distress syndrome (grade 3 or 4), need for intubation and mechanically assisted ventilation, intraventricular hemorrhage (grade 3 or 4), necrotizing enterocolitis (grade 3 or 4), proven sepsis diagnosed by culture, retinopathy of the preterm newborn requiring laser treatment (grade 3 or 4) and length of stay in the intensive care unit. Neonatal mortality will include any death before discharge from the hospital.

#### **3 Study Design**

## **3.1 General Design**

This is a multi-center, open-label, randomized study. Women with twin gestations presenting for routine prenatal ultrasound between 16 to 23 6/7 weeks will be offered the option of having their cervical length measured as part of the standard of care for screening of preterm birth. Women with TVU CL  $\leq$  25mm will be counseled about the risk of preterm birth and will be offered 400mg daily vaginal progesterone until 36 weeks of gestation. Those women with a cervix measuring  $\leq$  15mm will be invited to participate in the trial. Eligible subjects can be enrolled between 16 0/7 to 23 6/7 weeks gestation; subjects randomized to the use of the ultrasound indicated cerclage will have the procedure scheduled in the operating room under anesthesia. Decision to perform amniocentesis prior to the cerclage to rule out subclinical chorioamnionitis, surgical technique and suture type will be at the discretion of the

surgeon. Once the ultrasound indicated cerclage is in place, subjects will continue with their usual scheduled clinical prenatal visits, and will participate in the study until delivery. Cerclage will be removed during the 36th week of pregnancy on those asymptomatic women or earlier if indicated (preterm labor, PPROM, vaginal bleeding). Newborns will participate in the study until discharge home from the hospital. Information about pregnancy and neonatal outcomes will be obtained from medical records.

## 3.2 Primary Study Endpoints

Spontaneous preterm delivery at less than 34 weeks gestation

# 3.3 Secondary Study Endpoints

## Secondary effectiveness endpoints:

- Gestational age at delivery
- Interval between diagnosis and delivery
- Birth weight of each neonate
- Spontaneous preterm birth rates at less than 24, 28, 32 and 37 weeks gestation
- Spontaneous rupture of membranes before 34 weeks gestation

## Secondary safety endpoints:

- Admission to the NICU and length of stay if admitted
- Neonatal death before discharge from hospital
- Composite adverse neonatal outcome (includes any of the following: necrotizing enterocolitis (grade 3 or 4), Intraventricular hemorrhage (grade 3 or 4), respiratory distress syndrome (grade 3 or 4), need for intubation and mechanically assisted ventilation, retinopathy of the newborn requiring laser treatment (grade 3 or 4), and proven sepsis with positive culture).
- Clinical Chorioamnionitis
- Histological chorioamnionitis (It is standard of care to send placenta to pathology for multiple gestations).
- Significant adverse maternal effects including intraoperative rupture of membranes, bleeding, and cervical laceration (tear).

## 4 Subject Selection and Withdrawal

## 4.1 Inclusion Criteria

- 1. Pregnant women more than 18 years of age (limits the participants to female gender)
- 2. Diamniotic twin pregnancy
- 3. Asymptomatic
- 4. TVU CL  $\leq$  15 mm between 16-23 6/7 weeks gestation

[figure not shown]
## 4.2 Exclusion Criteria

- 1. Singleton or higher order than twins multiple gestation
- 2. TVU CL >16mm
- 3. Cervical dilation with visible amniotic membranes
- 4. Amniotic membranes prolapsed into the vagina
- 5. Fetal reduction after 14 weeks form higher order
- 6. Monoamniotic twins
- 7. Twin-twin transfusion syndrome
- 8. Ruptured membranes
- 9. Major fetal structural anomaly
- 10. Fetal chromosomal abnormality
- 11. Cerclage already in place for other indication
- 12. Active vaginal bleeding
- 13. Clinical chorioamnionitis
- 14. Placenta previa
- 15. Painful regular uterine contractions
- 16. Labor

#### 4.3 Subject Recruitment and Screening

- Potential study subjects will be identified at the time of a routine second trimester fetal ultrasound exam between 18 to 23 6/7 weeks gestation. All clinical sites have designated prenatal ultrasound units. Patients at all sites diagnosed with twin gestation will be offered transvaginal ultrasound cervical length for the screening of preterm birth. The initial consent to have a transvaginal ultrasound assessment of the cervical length will be a verbal consent as part of standard of care.
- Staff who will be performing screening TVU CL will be trained and certified through the Fetal Medicine Foundation https://fetalmedicine.org/training-n-certification/certificates-of- competence/cervical-assessment-1 or CLEAR (https://clear.perinatalquality.org/).
- 3. TVU CL technique: Endocervical canal length will be measured as the distance between the internal and external os using a vaginal probe at 6-MHz probe placed in the anterior fornix of the vagina. Three anatomic land- marks will define the appropriate sagittal view: the internal os, the external os and the endocervical canal. The image will be enlarged while visualizing the three landmarks simultaneously. Gentle pressure will be exerted on the cervix by the transducer followed by minimal pressure to allow visualization of the three landmarks. This procedure will be repeated three times and the shortest measurement will be recorded.
- 4. Women with TVU CL ≤ 25mm will be offered daily 400mg vaginal progesterone as standard of care based on recently published meta-analysis A repeat TVU CL will be offered a second time for those women with TVU CL 16 30 mm due to the concern for cervical length shortening over the next few weeks.

- 5. Women with TVU CL ≤15mm who will meet the inclusion criteria will be counselled by an obstetrician regarding the risk of SPTB as per standard of care. Only IRB approved research staff will approach eligible patients to assess interest in participating as well as to explain the trial. The patient will be given ample time to have all questions addressed and consider participation.
- 6. Women with a TVU CL <10mm will be offered a speculum exam (pelvic exam). If the cervix is dilated and amniotic membranes are visible, women would not be eligible for randomization in this clinical trial. A digital cervical exam will not be done routinely.
- 7. If the patient meets inclusion criteria and agrees to participate in the study, the informed consent form will be signed and a copy will be given to the patient.
- 8. Women who are eligible and consent to participate in the study will be randomly assigned to one of two groups: cervical cerclage (i.e. intervention group) or no cerclage (i.e. control group). A webbased system will be used to communicate the randomization assignments to the trial staff. Subjects will be randomized using blocks of randomly varying size (2, 4 and 6).
- For those patients assigned to cerclage, an insurance precertification process will be requested. After insurance approves the procedure, the cerclage will be scheduled in the operating room and it will be placed by one of the Maternal Fetal Medicine specialist and fellow.
- 10. If patient declined participation and she is stable, she will continue outpatient bi-weekly or monthly prenatal care visits as per standard of care.
- If patient elects to have expectant management without randomization, we will ask for her authorization to address the research protocol at a different opportunity during her prenatal visits until 23 6/7 weeks, after that gestational age she is no longer eligible for participation.

# 5 Study

# 5.1 Description

Cervical cerclage is a suture/tape surgically placed around the cervix as close as possible to the high of the internal os. This suture is a non-absorbable sterile material

# **5.2 Treatment Regimens**

Subjects will be randomized in a 1:1 fashion to either receive the ultrasound indicated cerclage, or expectant management. Women will still be able to withdrawal from the study after randomization if they feel that either expectant management or cerclage have an unacceptable risk of extreme premature delivery with increased risk of a severely handicap children.

# 5.2.1 Ultrasound indicated cerclage

For those randomized to ultrasound indicated cerclage placement, the surgical procedure will be scheduled in the main operating room under anesthesia.

# 5.2.2 Expectant management

For those randomized to expectant management, they will continue routine pregnancy care: daily vaginal progesterone and surveillance for signs of preterm labor.

# 5.3 Method for Assigning Subjects to Treatment Groups

A computer system will be used to communicate the randomization assignments to the trial staff. Subjects will be randomized centrally using blocks of randomly varying size (e.g, 2, 4 and 6).

## 5.4 Placement of Cerclage

Ultrasound indicated cerclage is placed by trained physician in the operating room under anesthesia (regional or general at the discretion of the anesthesiologist). Amniocentesis to evaluate for subclinical chorioamnionitis will be offered to every patient, declining amniocentesis doesn't exclude subjects from participation in this trial. Amnioreduction (removal of larger amount of amniotic fluid), surgical technique, election of sutures, and admission to the hospital for observation or recommended amount of maternal physical activity after randomization will be at the discretion of the attending physician performing the cerclage. Women randomized to the cerclage group will receive indomethacin 50mg orally before the cerclage and for three additional doses postoperatively every 8 hours (at 8h, 16h, and 24h after the cerclage). Women randomized to the cerclage group will also receive one dose of cefazolin 1g IV (or 2g if >80kg) before the cerclage.

# **6 Study Procedures**

## 6.1 Transvaginal cervical length measurement

Potential study subjects will be identified in the ultrasound room. Transvaginal ultrasound cervical length will be offered at the time of a routine second trimester fetal anatomy ultrasound exam between 16-23 6/7 weeks gestation as part of standard of care practice for twin pregnancies, verbal consent will be requested prior to transvaginal ultrasound.

# 6.2 Randomization

Patients with TVU CL ≤ 15mm who are eligible and consent to participate in the study will be randomly assigned to one of two groups: Ultrasound indicated cerclage or no cerclage (standard expectant obstetric management). Subjects will be randomized using random block sizes of 2, 4 or 6. Patients allocated to the ultrasound indicated cerclage group will have the cerclage surgically placed.

# **6.3 Interim Contacts**

Patients in both groups will be contacted by the research assistants monthly either by phone or in person at the time of their prenatal visit. The research assistants will ask the patients if they have had any complications with their pregnancy including any evaluations and/or admissions for preterm labor, vaginal bleeding, leaking of amniotic fluid, vaginal discharge and/or discomfort of if they received medications like antenatal steroids for fetal lung maturity, tocolysis or magnesium sulfate infusion. Consents for release of medical information will be signed at the time of randomization to gather medical information pertinent to the study in case of admissions to other institutions.

Patients will be instructed to report any adverse symptoms including pain, vaginal bleeding, uterine contractions, decreased fetal movements and leakage of amniotic fluid immediately. They will be given a phone number to call if they have any questions or concerns about the study. A physician who is knowledgeable about the study will be available at all times. The study investigator will communicate with the patient's primary obstetrician; ultrasound indicated cerclage placement will be done by one of the study investigators, but removal at any time during pregnancy can be done by the primary obstetrician. The primary obstetrician will be responsible for all prenatal care and delivery.

## 6.4 Cerclage Removal

The cerclage will be removed by the primary obstetrician during the 36th week of gestation if asymptomatic. Removal of cerclage can be performed in the office or triage room; there is no need of anesthesia. Indications for cerclage removal before this time include: active vaginal bleeding, persistent uterine contractions despite tocolysis, ruptured of amniotic membranes, and prolapsed membranes through the cervix / suture.

## 6.5 Pregnancy Outcome

After subjects have delivered, information regarding outcome of the pregnancy and neonatal outcome until discharge home will be abstracted from the subjects' medical records. A release of medical records consent will be signed at the time of randomization, in case the patient delivers at an outside institution.

#### **7** Statistical Plan

## 7.1 Sample Size Determination

Calculation of sample size was based on a reduction in the incidence of spontaneous delivery before 34 weeks from 70% in the expectant management group to 50% in the cerclage group, with a power of 80%. To detect this difference at a significance level of 5%, we will need to enroll a total of 186 subjects with 93 subjects in each arm, plus 10% for loss of follow up. Total 200 subjects with 100 subjects in each arm

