## 7.2 Statistical Methods

The primary outcome is spontaneous preterm birth before 34 weeks of gestation. Secondary outcomes include gestational age at delivery, interval between diagnosis and delivery, birth weight, spontaneous preterm birth rates at less than 24, 28, 32 and 37 weeks gestation and spontaneous rupture of membranes at less than 34 weeks gestation. Secondary safety outcomes include admission to NICU, neonatal death, length of stay in the NICU until discharge home, composite adverse neonatal outcome that includes necrotizing enterocolitis (stage 3 or 4), intraventricular hemorrhage (grade 3 or 4), respiratory distress syndrome (grade 3 or 4), need of intubation and mechanical ventilation, retinopathy of prematurity requiring laser treatment (stage 3 or 4) and proven sepsis requiring treatment), and significant adverse maternal effects will include: intraoperative rupture of membranes, clinical or histological chorioamnionitis, postpartum hemorrhage, cervical tear and uterine rupture). Neonatal mortality prior to discharge home form the hospital.

Statistical analysis will be based on the intention-to-treat principle. Comparisons between the two groups will be made with the Mann-Whitney U test. Univariate comparisons of dichotomous data will be performed with Fishers exact test. The p values for all hypotheses will be two sided, and p values of less than 0.05 will be considered to be significant. The risk of spontaneous preterm birth before 34 weeks will be quantified by use of the relative ratio and 95% confidence interval. Multivariate analysis will be performed using logistic regression. The risk of spontaneous preterm birth from randomization until delivery will be assessed with Kaplan-Meier analysis, in which gestational age is the timescale, spontaneous delivery is the event, and elective deliveries are censored. SPPS software package (version 16.0) will be used for all statistical analyses.

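### The 80% power in 7.1 does not hold for Fisher's exact test, the only test 7.2 names for binary outcomes, and 200 women cover 7% loss, not the stated 10%

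*Combined protocol and SAP*

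**What the plan says.** Section 7.1 (Sample Size Determination) assumes that spontaneous delivery before 34 weeks falls from 70% under expectant management to 50% with cerclage, with 80% power and a 5% significance level. It names no test. It concludes that "we will need to enroll a total of 186 subjects with 93 subjects in each arm, plus 10% for loss of follow up", and closes with "Total 200 subjects with 100 subjects in each arm".

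Section 7.2 (Statistical Methods) gives the testing rule for all binary outcomes in one general sentence: "Univariate comparisons of dichotomous data will be performed with Fishers exact test". It adds: "The p values for all hypotheses will be two sided, and p values of less than 0.05 will be considered to be significant". The sentence specific to the primary outcome concerns estimation: "The risk of spontaneous preterm birth before 34 weeks will be quantified by use of the relative ratio and 95% confidence interval". Logistic regression is listed as the multivariate analysis, without a stated outcome or covariates. No chi-square test appears.

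Two other sections bear on how much loss to expect. Section 6.5 (Pregnancy Outcome) provides for retrieval of outside records: "A release of medical records consent will be signed at the time of randomization, in case the patient delivers at an outside institution". Section 5.2 (Treatment Regimens) says: "Women will still be able to withdrawal from the study after randomization".

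**The concern.** There are two separate points.

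First, a power figure belongs to a particular test. The 93 per arm comes from a formula without continuity correction, whereas the one test 7.2 offers for a binary outcome is Fisher's exact test. Fisher is conservative at these sample sizes, so it has less power than that formula implies. If it is the primary test, the trial is less likely to detect the targeted effect than 7.1 states, and a null result would be read as slightly stronger evidence than it is.

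Second, the loss allowance does not add up: 200 is not 186 plus 10%.

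Because the primary test has to be inferred, the choice between Fisher and chi-square also stays open, and the two can disagree near p = 0.05.

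**Working it through.** **Inputs.** Control rate 0.70, cerclage rate 0.50, power 0.80, alpha 0.05, 93 per arm before loss, 10% loss and 200 in total, all from 7.1. Two-sided testing and Fisher's test are from 7.2. The 1:1 allocation is from 5.2.

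**1. Reproducing 93 per arm.** Pooled normal formula without continuity correction, with mean rate 0.6:

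n = [1.95996·√(2·0.6·0.4) + 0.84162·√(0.7·0.3 + 0.5·0.5)]² / 0.20²
= [1.3579 + 0.5708]² / 0.04 = 92.999, so 93.

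The arcsine formula gives 92.7, also 93. The continuity-corrected formula, which approximates Fisher's test, gives 102.8, so 103. The plan's figure is therefore correct for an uncorrected test.

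**2. Exact power at fixed arm sizes.** For every pair of event counts, the two binomial probabilities (0.7 control, 0.5 cerclage) are multiplied, then summed over the tables where the two-sided p value is below 0.05.

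| Control / cerclage | Fisher | Uncorrected Pearson |
|---|---|---|
| 90 / 90 | 74.9% | 79.3% |
| 93 / 93 | 75.1% | 79.9% |
| 94 / 92 | 76.4% | 79.4% |
| 92 / 94 | 78.3% | 80.3% |
| 100 / 100 | 79.2% | 83.2% |
| 102 / 102 | 80.6% | 84.3% |

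With equal arms, Fisher first reaches 80% at 102 per arm. Its power moves in steps and depends on the exact split. With 186 evaluable women and arms up to 10 apart, it ranges from 75.1% to 78.3%. In some nearly complete splits it exceeds 80% (81.3% at 100/99, 81.8% at 98/100).

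**3. Averages starting from 200 enrolled.** Each woman is assumed lost independently, at the same rate in both arms.

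| Loss | Fisher | Uncorrected Pearson |
|---|---|---|
| 0% | 79.2% | 83.2% |
| 1% | 80.0% | 82.6% |
| 2% | 79.6% | 82.2% |
| 5% | 78.0% | 81.0% |
| 7% | 77.3% | 80.2% |
| 10% | 76.5% | 78.9% |

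If instead exactly 14 of 200 are lost and split at random between arms (186 left), Fisher averages 76.8%. If exactly 20 are lost (180 left), it averages 76.5%.

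**4. Loss allowance.** 186 × 1.1 = 204.6, so 205. 186 / 0.9 = 206.7, so 207. With 200 enrolled, the largest loss that leaves 186 is 1 − 186/200 = 7.0%. At 10% loss, 200 × 0.9 = 180 remain, 6 short of the plan's own requirement.

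**The case against.** **Fisher is inferred, not designated.** This is true. The only analysis 7.2 ties by name to the primary outcome is the relative ratio with its confidence interval. If success were judged by whether a Wald interval for the log relative risk excludes 1, exact power would be 79.1% at 93/93, 77.7% at 90/90 and 83.0% at 100/100, so the stated 80% would nearly hold. But 7.2 presents that interval as a way to quantify the risk, not as a test, and the Study Summary names the odds ratio instead. Fisher is the only named test that fits a binary outcome. If it is not intended, the primary test is unspecified, and the remedy is still to name it.

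**75.1% is the worst case.** Also true. It is the lowest of the eleven splits of 186 with arms up to 10 apart. The averages of about 77% are the fairer summary.

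**The gap is small beside the uncertainty in the 70% and 50% assumptions.** This stands. The retrospective cohort in section 1.2 behind the short-cervix hypothesis found 76.9% versus 46% in only 71 women, so a few points of power are not decisive. Loss may also be low, because outcomes are abstracted from records under a signed release. These arguments keep the point minor. They do not make the stated figures correct.

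**The loss slip is only 5 to 7 women.** Agreed, but it depends on no assumption about the test: 10% and 200 cannot both be right.

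**Conclusion.** Both points hold, and both are minor. The 93 per arm is not a miscalculation; the test behind it differs from the one test 7.2 names for binary data.

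Read with Fisher as the primary test, and with loss independent and equal in both arms, the average chance of missing a true 70% versus 50% difference is 21% with no loss, 22% at 5%, 23% at 7% and 23.5% at 10%, against the stated 20%. The shortfall from 80% is under 1 point at 0–2% loss and averages about 3 points at 7–10%. It is about 5 points if the arms end exactly equal at 93/93 or 90/90. Under an uncorrected chi-square test the stated 80% is essentially right at 93/93 (79.9%).

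Independently of the test, 200 women allow for 7% loss. Nothing here biases the estimate or inflates type I error. The consequence is a slightly overstated power and a primary test left to inference.

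**What to change.** No added enrolment is needed. In 7.1, say that 200 women allow for 7% loss. In 7.2, name the test for the primary outcome, in one of two ways.

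- **Keep Fisher.** Restate power in 7.1 as about 79% with no loss, 78% at 5%, 77% at 7% and 76.5% at 10%, assuming independent loss at the same rate in both arms (74.9% if the arms end at exactly 90/90). The cost is a slightly less favourable stated power.
- **Name the uncorrected Pearson chi-square as primary**, and keep Fisher for sparse secondary outcomes. Do this only if the decision is made before outcome data are seen. State power as about 83% with no loss, 81% at 5%, 80% at 7% and 79% at 10%. Disclose that the exact size can slightly exceed 5%: for common event rates of 50–70% it reaches 5.6% at 100/100 and 5.3% at 90/90, and it averages about 5.05% with 5–10% loss. The cost is that small excess, which Fisher avoids.

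The first is the simpler repair and changes no analysis. Both are edits to 7.1 and 7.2 only, with no extra patients or data.
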